***Note the IRB-approved study protocol for the parent study above was utilized for this ancillary study:**

Title: Utilizing Protein During Weight Loss to Impact Physical Function and Bone

NCT03819478

Scientific Study Title: Long-term effects of weight loss and supplemental protein on physical function

Lay Title: UPLIFT (Utilizing Protein During Weight Loss to Impact Physical Function)

Principal Investigator: [name]

Co-investigator(s): [name], [name], [name], [name], [name]

Sponsor or funding source: NIH/NIA

Background, Rationale and Context

Obesity exacerbates age-related declines in physical function and is a strong determinant of mobility disability.¹⁻³ One-third of older adults are obese;⁴ thus, there is an urgent need to identify effective therapies that prevent obesity-related declines in physical function. The loss of lean mass with age contributes to age-related declines in physical function.⁵⁻⁷ Since approximately one-fourth of lost weight is comprised of lean mass,⁸⁻¹¹ current weight loss recommendations regarding macronutrient composition – and protein in particular – during caloric restriction may exacerbate the loss of lean mass in older adults, further compromising physical function over the long-term. Moreover, studies suggest that older adults need more protein to elicit the same stimulatory effect on muscle protein synthesis and maintain lean mass than younger adults.¹²⁻¹⁶ Thus, recommendations for effective weight loss treatments that preserve lean mass and optimize function in obese older adults may differ from those for younger adults. Additionally, recent *Guidelines (2013) for the Management of Overweight and Obesity in Adults* stated “there is a need for further research to understand the most appropriate strategies and prescriptions for weight loss [in] older adults.”¹⁷

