Individuals who meet all eligibility criteria and provide informed consent will be randomized to one of the three intervention groups (following all baseline testing) using a web-based randomization scheme (developed by [name]) with blocking stratified by sex. Block size and the randomization sequences will be unknown to the research staff. Treatment assignment will be generated using a program that the study coordinator will access from her PC via the study website. Individuals with abnormal results at screening will be referred to their physicians.

Study Interventions

6-month weight loss intervention:

Caloric restriction and behavior modification/nutrition education: All participants will undergo a dietary weight loss intervention designed to elicit behavioral changes leading to decreased caloric intake sufficient to yield a ~10% loss of initial body mass. Recommended weight loss interventions for obese older adults include moderate caloric restriction (CR) to elicit a weight loss of 0.5-1 kg/wk.^{1;34-36} Thus, the 6-month weight loss

intervention is designed to elicit ~0.5 kg/wk weight loss through a CR level of -500 kcal/d, plus an exercise prescription that meets current American Heart Association (AHA) and American College of Sports Medicine (ACSM) physical activity recommendations for older adults (described below).³⁷ With a calorie deficit of 500 kcal/d, we expect total weight loss of ~10.0 kg. The reduced calorie level is derived by subtracting 500 from each persons estimated daily energy needs for weight maintenance. Individual energy needs are calculated from the direct measurement of resting metabolic rate and applying an activity factor based on a description of their daily activities (typically 1.3 for sedentary persons). No woman will be recommended <1100 kcals/d and no man <1300 kcals/d.

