Baseline visit 2 (BV2) will take place approximately 1 week after the BV1 visit in the morning (after an 8 hour overnight fast). Participants will have their weight and blood pressure measured. Then participants will have their resting metabolic rate (RMR) assessed for the purpose of estimating each person's baseline calorie level. Participants will also undergo tests to assess arterial stiffness, including aortic augmentation index (AIx) and arterial wave reflection magnitude. Participants will then have blood drawn for glucose, insulin, HbA1c, lipids, and storage. The first of three 24-hr dietary recalls will be administered to introduce and train the participant for the procedures used in subsequent 24-hr dietary recalls done by phone (in the event that scheduling precludes

administration of the first 24-hr dietary recall in person, the participant will be given written instructions and the first 24-hr dietary recall administered by phone). Two additional 24-hr diet recalls will be administered by phone following BV2 but prior to the participant's first intervention visit. (24-hr diet recalls may be started at BV1 for some participants to ensure they are completed prior to the start of intervention.) Following all fasting measures, participants will be given a snack. Medical history and current medications and dietary supplements will be reviewed. The 24-hour urine sample will be collected to measure urinary nitrogen and creatinine for estimating dietary protein intake and for storage.

Randomization/first intervention visit. Due to the group nature of the diet classes, participants will be randomized in waves with all participants starting intervention in a given week. The study interventionist will check to see which intervention group the participant is randomized to at their first meeting with each eligible participant during the first week of each wave's intervention.

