Sample size: The sample size chosen for this study (n=225; 75/group) will provide $\geq 80\%$ power ($\alpha=0.05$) to detect clinically meaningful effects of a higher protein / lower CHO diet during weight loss and follow-up on physical function (with estimated retention of 80% or 60 completers per group; see **Table 3**). Baseline standard deviations and pre-post correlations used for power analyses were calculated using data from obese older adults from our OPTIMA study¹¹ – a weight loss study with the same inclusion/exclusion criteria as the proposed study. Standard deviations were assumed to be similar between groups. The mean group differences we can detect correspond to an absolute change from average baseline values of these measures in obese older adults of 0.2 points for the expSPPB and 12.6 Nm for muscle strength. Differences of 0.12 points and 0.22 points on the expSPPB have been shown to be small and large clinically meaningful differences, respectively.⁶³ Even with a conservative drop-out rate of 20%, 60 participants/group provides $\geq 80\%$ power (overall $\alpha=0.05$, 2-sided tests for 3 comparisons) to detect between group differences for primary and secondary outcomes over 18 months. In response to our NIA-appointed DSMB, we have recalculated the power based on the actual number of participants enrolled (total n=187 or ~ 50 per group after accounting for the 20% drop-out rate) using the same baseline standard deviations and pre-post correlations from obese older adults in our OPTIMA study noted above.

Table 3. Power to detect significant differences in mean change between groups with ANCOVA ($\alpha=0.05$ after Bonferroni correction for each outcome; 2-sided test), assuming similar SD between groups

Outcome measure	Group Comparison	Pre-Post Correlation	Standard Deviation (SD)	Mean group difference	Effect Size (diff/SD)	Power for Analysis of Covariance (n per group)			
						n=60	n=65	n=75	n=50
ExpSPPB (points)	RecProt vs. 6mo HiProt	0.72	0.5	0.20	0.41	80	84	89	71
	6mo vs. 18mo HiProt			0.20	0.41	80	84	89	71
	RecProt vs. 18mo HiProt			0.41	0.82	>99	>99	>99	>99
Knee extensor strength (Nm)	RecProt vs. 6mo HiProt	0.77	32.8	12.6	0.38	81	84	90	72
	6mo vs. 18mo HiProt			12.6	0.38	81	84	90	72
	RecProt vs. 18mo HiProt			25.3	0.77	>99	>99	>99	>99
Lean mass (Kg)	RecProt vs. 6mo HiProt	0.99	12.0	1.1	0.09	86	89	93	78
	6mo vs. 18mo HiProt			1.1	0.09	86	89	93	78
	RecProt vs. 18mo HiProt			2.2	0.18	>99	>99	>99	>99

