Data analysis: Initial analyses will follow the “intent-to-treat” principle in which data from all randomized participants are analyzed according to their randomized groups. Analysis of covariance (ANCOVA) will be used for both primary and secondary aims to compare the group effect on change in expSPPB and muscle strength (primary aim) and weight loss maintenance, total and appendicular lean mass and fat-to-lean mass ratio, and thigh muscle volume and inter-muscular adipose tissue (IMAT) (secondary aim) at 18 months. Group contrasts will be constructed and tested within each model. ANCOVA will also be used to compare physical function, weight and body composition at 6 months. To explore whether differences in lean mass mediate the effect of a higher protein diet during and subsequent to weight loss on physical function, change in lean mass will be added to the ANCOVA models to assess whether the intervention effect is reduced or eliminated as an ad hoc mediation analysis. To compare the exploratory outcomes (bone mineral density and cardiometabolic risk factors) at 6 and 18 months, ANCOVA with repeated measurements will be used, and correlations between 6 and 18 months taken into account using a compound symmetry covariance structure. All models will be adjusted for the baseline measure, age, gender, and race.

Factors that may influence the measured responses to the interventions (e.g., initial body weight or composition, changes in weight, physical activity, etc.) will be evaluated and possibly included in secondary analyses. We will also consider conducting analyses adjusted for intervention process measures (such as dietary intake, average attendance at diet and exercise sessions, and protein intake/urinary nitrogen) to examine the extent to which these contribute to the outcomes.

Planned sensitivity analyses to assess the impact of COVID19: Because of the potential impact of COVID19 on intervention delivery and follow-up assessments, we plan to conduct several sensitivity analyses:

- 1) Exclude Wave 13 and 14 participants (n=26) whose intervention was interrupted by the COVID19 research pause on March 13, 2020, and who completed the last ~2 and ~4 months, respectively, of the exercise portion of the 6-month intervention on their own while attending the diet portion of the intervention remotely (via phone).

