- 2) Exclude Wave 13-17 participants (n=63) whose intervention was interrupted by COVID19 (Waves 13 and 14; see above) or whose intervention was modified from earlier waves to accommodate safety measures put in place due to COVID19 (Waves 15-17; center-based exercise reduced from 3x/week to 1-2x/week after week 6 to allow for physical distancing).
- 3) Exclude Wave 7 participants (n=15) and participants from Wave 6 (n=5) whose 18-month visits were 2-3 months out of window due to the COVID19 research pause and phased restart of in-person research.

Missing data considerations: We will document withdrawal and compliance in detail to permit the formulation of reasonable assumptions regarding missing observations. If it is determined that our outcomes are missing at random (MAR), we will attempt to identify baseline covariates that predict attrition and use these covariates to impute missing data based on multiple imputations (MI) and draw inferences based on MI. If it is determined that our outcomes are not missing at random (MNAR), sensitivity analyses MNAR assumptions will be carried out using MI following the recommendation of Molenberghs and Kenward.⁶⁴

Human Subjects Protection

Subject Recruitment Methods: We will recruit individuals using community-based recruitment strategies including newspaper ads and mass mailings. We will also advertise in the Aging Center's VITAL newsletter and participate in community outreach events.

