Statistical Analysis Plan

Title: Utilizing Protein During Weight Loss to Impact Physical Function and Bone

NCT03819478

Date: 04/24/2023

Statistical Analysis Plan

We expect to enroll 225 participants in the study. Retention is expected to be $\geq 90\%$ at 6 months (≥ 67 completers/group) and $\geq 80\%$ at 18 months (≥ 60 completers/group) based on compliance rates of prior weight loss and exercise trials conducted at the Wake Forest School of Medicine (WFSM). All statistical analyses will be performed in SAS or R. Before performing hypothesis testing, data distributions will be examined to determine if transformations are necessary and if nonparametric approaches should be used. Analyses will conform to intent-to-treat principles, indicating that participants will be included in analyses according to the groups to which they were randomized. The models will include a random effect for wave to account for the potential correlation of participants within waves.

Volumetric BMD and Cortical Thickness Outcome Measures at Primary Endpoint of 18 months

The study is $\geq 80\%$ powered ($N=180$, 2-sided $\alpha=0.025$) to detect differences in change between groups of 0.016 g/cm^3 ($SD=0.028$ g/cm^3) and 0.007 g/cm^3 ($SD=0.013$ g/cm^3) volumetric bone mineral density (vBMD) and 0.063 mm ($SD=0.111$ mm) and 0.018 mm ($SD=0.032$ mm) cortical thickness at 18 months at the spine and hip, respectively (SDs of change from preliminary data).¹ Mean group differences and effect sizes at 80% power are reported in **Table 1** for the expected 18-month sample size ($N=60/\text{group}$), as well as smaller sample sizes in the event of shortfalls in enrollment or retention ($N=30$, 40 , and $50/\text{group}$). Effect sizes ≥ 0.80 have been observed in prior trials that have detected statistically significant differences in lumbar spine BMD (0.92 - 1.60 effect sizes)²⁻⁴ and hip BMD (0.80 effect size)^{2,3} between higher versus lower protein groups, suggesting that our study is adequately powered to detect differences even with $N=30/\text{group}$.

We will use analysis of covariance (ANCOVA) to compare group effects on vertebral and femoral vBMD and cortical thickness at the primary endpoint of 18 months, with adjustment for baseline values. Age, sex, race, and baseline value of the outcome of interest will be adjusted for as covariates in these analyses.

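### The parent protocol's ANCOVA models leave out wave, although participants are randomised and treated in waves; adding it would be a small, nearly free gain in precision for the primary outcome

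*Protocol*

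**What the plan says.** The protocol's Data analysis section uses ANCOVA for the primary and secondary aims at 18 months and for the 6-month comparisons. It ends the model description with: "All models will be adjusted for the baseline measure, age, gender, and race".

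Under Randomization/first intervention visit, the protocol says: "Due to the group nature of the diet classes, participants will be randomized in waves with all participants starting intervention in a given week". The scheme is described under Participant screening and randomization as web-based, "with blocking stratified by sex". Wave is not named as a stratum and the block size is not disclosed.

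The section on COVID19 sensitivity analyses shows that waves differed in delivery. Waves 13 and 14 (26 participants) were interrupted. Waves 15 to 17 are those "whose intervention was modified from earlier waves to accommodate safety measures put in place due to COVID19". Together these are 63 of the 187 enrolled (34%). Wave 7 (15 participants) and 5 participants from Wave 6 had 18-month visits 2 to 3 months out of window. The three planned analyses exclude these groups in turn; none changes the primary model.

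The SAP's opening paragraph says: "The models will include a random effect for wave to account for the potential correlation of participants within waves". Its scope is volumetric BMD, cortical thickness, marrow fat and bone strength. The protocol opens by stating its own relation to that work: "Note the IRB-approved study protocol for the parent study above was utilized for this ancillary study".

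**The concern.** A wave is a calendar cohort that starts in the same week and attends mostly group sessions. Outcomes within a wave may therefore be correlated, and the COVID period gives a concrete reason for waves to differ in level. The investigators accept this for the bone outcomes. The same participants, waves and classes produce the expSPPB and strength data, yet those models carry no wave term.

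What is at stake is precision. Randomisation operates within waves, so a good part of each arm comparison is a within-wave comparison. Leaving wave out puts between-wave variance into the residual. This matters most for the two adjacent expSPPB contrasts (RecProt vs 6-mo HiProt, and 6-mo vs 18-mo HiProt). The protocol's own recalculation gives them 71% power, and the ordered primary hypothesis depends on both.

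**Working it through.** **Inputs.** From Protocol Table 3 for expSPPB: SD 0.5, pre-post correlation 0.72, effect size 0.41 (so a difference of 0.41 × 0.5 = 0.205 points, printed as 0.20). Alpha is 0.05 overall with "2-sided tests for 3 comparisons", so 0.05/3 = 0.0167 per contrast and critical z = 2.394. Sample size: 187 × 0.80 / 3 = 49.9, about 50 per group.

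**Assumptions not in the documents.** A wave ICC (ρ, the between-wave share of baseline-adjusted variance) of 0.02 to 0.10, and 17 waves of similar size (17 is the highest wave number mentioned), which gives 150/17 ≈ 8.8 completers per wave. The ICC is treated as known.

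**Reproducing the stated power.** ANCOVA SD = 0.5 × √(1 − 0.72²) = 0.347. Noncentrality at 50 per group = 0.205 / (0.347 × √(2/50)) = 2.95. Power = Φ(2.95 − 2.394) = 71.2%, against 71% stated. The same formula gives 80.0, 83.5 and 89.0% at 60, 65 and 75 per group, against 80, 84 and 89%.

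**Gain if arms are balanced within every wave.** The contrast is then wholly within waves. Omitting wave widens the SE by 1/√(1 − ρ) − 1, and modelling it multiplies the noncentrality by 1/√(1 − ρ).

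**Gain if allocation ignores wave.** About b = (17 − 1)/(150 − 1) = 0.107 of the contrast then lies between waves. With wave modelled, relative information is (1 − b)/(1 − ρ) + b/(1 + 7.8ρ). For ρ = 0.05 this is 0.893/0.95 + 0.107/1.39 = 0.940 + 0.077 = 1.017, so the SE ratio is √1.017 = 1.008. The generalised least-squares variance under random allocation agrees closely and gives the figures below.

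| Assumed ICC | SE widening, balanced | Power with wave, balanced | SE widening, unrestricted | Power with wave, unrestricted |
|---|---|---|---|---|
| 0 | 0 | 71.2% | 0 | 71.2% |
| 0.02 | 1.0% | 72.2% | 0.2% | 71.4% |
| 0.05 | 2.6% | 73.8% | 0.8% | 72.0% |
| 0.10 | 5.4% | 76.4% | 2.5% | 73.7% |

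Blocking within sex should place the trial between the two cases. Even with exact balance, an ICC of about 0.17 is needed to reach 80%.

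The table assumes that the planning SD already contains wave variance. If wave variance comes on top of it (balanced case), leaving wave out lowers power from 71.2% to 70.2, 68.6 and 65.9% at ICC 0.02, 0.05 and 0.10. The loss is of the same order.

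**Validity.** With wave effects shared by the arms, a small simulation without a wave term kept type I error at about 1.4 to 1.8% against the nominal 1.67%. In the limit of exact balance at ICC 0.10 it is 2 × [1 − Φ(2.394/√0.90)] ≈ 1.2%, which is conservative.

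**If diet classes are arm-specific.** With about 3 completers per arm in each wave and a wave-by-arm ICC of 0.05 to 0.10, the variance of an arm mean is inflated by 1 + (3 − 1)ρ = 1.10 to 1.20. A model that ignores this has type I error of about 2 × [1 − Φ(2.394/√1.10)] = 2.2% to 2 × [1 − Φ(2.394/√1.20)] = 2.9%. Simulation gave 2.4 to 3.5%, whether or not a wave main effect was in the model.

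**The case against.** The strongest objection is scope. A reader might infer that the SAP and protocol give conflicting rules for the primary model. They do not: the SAP covers the ancillary bone outcomes and sets no rule for expSPPB, strength or body composition. This objection stands. The SAP shows only that the investigators consider wave correlation relevant in this cohort. The two plans do overlap on volumetric BMD, which the protocol lists as a tertiary outcome and would model without wave.

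Second, the test is valid without wave when wave effects are shared by the arms. This also stands, so the point concerns efficiency, not bias. Nor can one say without qualification that the intervals are too wide. The documents do not say whether classes mix arms. If they do not, the intervals are too narrow, and a wave intercept alone would not correct them.

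Third, the ICC is assumed and the gain may be close to nil. That is correct at the low end of the range.

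Fourth, it is tempting to call the whole primary analysis underpowered. Table 3 supports that for the two adjacent contrasts only; RecProt vs 18-mo HiProt is above 99%, and the protocol itself discloses the 71%.

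Fifth, a reader might see a wave term as a substitute for the COVID exclusions. It is not. A random intercept absorbs level shifts common to the arms; the exclusions ask whether altered delivery or late visits changed the treatment comparison.

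What survives is that wave is a known design feature, it is missing from the covariate list, and including it costs almost nothing.

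**Conclusion.** The point holds as a modest, inexpensive improvement. Under an assumed wave ICC of 0.02 to 0.10 and effects shared by the arms, omitting wave widens standard errors by about 0.2 to 2.5% with unrestricted allocation and by about 1 to 5% with arms balanced within waves. This is roughly 0 to 5 power points on the two adjacent expSPPB contrasts, and nothing at an ICC of zero. It does not bias the primary test, and correcting it would not by itself bring those contrasts to 80%. The size rests on the assumed ICC, about 17 waves of similar size and 20% dropout. The direction rests on wave effects being common to the arms; with arm-specific classes the larger issue is clustering within class.

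**What to change.** In the protocol's Data analysis section, extend the sentence "All models will be adjusted for the baseline measure, age, gender, and race" by adding: with a random effect for wave. Apply it to the primary, secondary and 6-month models, in line with the SAP.

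State whether diet classes mix arms. If classes are arm-specific within a wave, also account for class (wave-by-arm) clustering, because a wave effect alone would leave the standard errors too small.

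Keep the three COVID exclusion analyses as planned.

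The cost is one phrase in the protocol and one line of code, with no new data or participants. The downside is one more variance component, estimated from about 17 waves.

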The **6-month follow-up visit (FV1/2)** will take place following week 26 of the intervention in the morning after an 8 hour overnight fast. Participants will have their weight and blood pressure measured. Then participants will have their resting metabolic rate (RMR) measured for the purpose of estimating each person's weight maintenance calorie level. The participant will also undergo tests to assess arterial stiffness. Blood will be drawn for glucose, insulin, HbA1c, lipids, CMP and CBC, and storage. Participants will then be provided with a snack. Any changes to medical history and current medications and dietary supplements will be reviewed. Whole-body, AP spine, and hip DXA scans will be done. The participant will have anthropometric measurements taken at their waist, hip and thigh. Lower extremity muscle strength (BiodeX dynamometer), grip strength, physical performance (expSPPB), and 400-m walk time will be measured. The MAT-sf and DSST will be administered. The CHAMPS Physical Activity Questionnaire, CES-D, SF-36, and FACIT questionnaires will be administered at the visit time permitting or by phone after the completion of the in-person visit. A series of CT scans (abdomen, hip and thigh) will be done. Participants will be given the 24-hr urine collection bottle and instructions for collecting urine to measure urinary nitrogen and creatinine for estimating dietary protein intake and for storage. Three 24-hr diet recalls will be administered by phone during the FV1/2 visit window. . Participants will schedule to drop off their 24-hour urine sample following their FV1/2 visit

Monthly phone calls: Participants will be called once a month during the 12-mo follow-up to ensure those that are in the 18-mo HiProt are continuing to consume the protein supplement. All participants will be asked about any health changes, injuries, etc., that may have occurred and any events recorded using the Adverse Event Form.

The **12-month follow-up visit (FV3)** will take place following week 52 of the intervention. Participants will have their weight and blood pressure measured. Lower extremity muscle strength, grip strength, physical performance (expSPPB), and 400-m walk time will be measured. The CHAMPS Physical Activity Questionnaire, MAT-sf, CES-D, SF-36, and FACIT questionnaires will be administered. Medical history and current medications and dietary supplements will be reviewed.

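### For 18-month function and body composition, the imputation rule names only baseline predictors, and the not-at-random sensitivity analysis is not guaranteed to run

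*Protocol*

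**What the plan says.** The protocol's Missing data considerations paragraph is the only missing-data rule in the supplied documents for function and body composition. It starts from records: "We will document withdrawal and compliance in detail to permit the formulation of reasonable assumptions regarding missing observations". It then has two branches. If outcomes are judged MAR, "we will attempt to identify baseline covariates that predict attrition and use these covariates to impute missing data based on multiple imputations (MI". On the other branch, "If it is determined that our outcomes are not missing at random (MNAR), sensitivity analyses MNAR assumptions will be carried out using MI". No criterion is given for choosing between them.

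Under Data analysis, ANCOVA is used "to compare the group effect on change in expSPPB and muscle strength (primary aim" and, for the secondary aim, on weight and body composition at 18 months. All models adjust for the baseline measure, age, gender and race. Repeated measures are planned elsewhere: "To compare the exploratory outcomes (bone mineral density and cardiometabolic risk factors) at 6 and 18 months, ANCOVA with repeated measurements will be used".

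Interim data exist. Outcome Measures lists function at baseline, 6, 12 and 18 months, and at the 12-month visit "Lower extremity muscle strength, grip strength, physical performance (expSPPB), and 400-m walk time will be measured". DXA and CT body composition is measured at baseline, 6 and 18 months.

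The SAP covers bone outcomes and has no missing-data section.

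**The concern.** There are two separate gaps.

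**Predictors.** The imputation model is described by baseline variables that predict attrition. Arm and the participant's own later scores are not named, and the analysis model does not use those scores either. Someone who reached month 6 or 12 and then left would be imputed as if those visits had not happened. If leaving depended on early response, and did so differently by arm, the 18-month contrast would be biased although the data to correct it had been collected.

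**Trigger.** The not-at-random (MNAR) analysis runs only after a finding that outcomes are MNAR. Withdrawal and compliance records can inform that judgement, but neither they nor the observed outcomes can settle it, because the distinction concerns values nobody saw. The MAR branch carries the same condition. Readers are therefore not assured of seeing how far the 18-month result depends on the unobserved participants.

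**Working it through.** **Inputs** (Protocol, Sample size and Table 3, unless noted)
- expSPPB: SD 0.5, pre-post correlation 0.72, effect size 0.41 for adjacent groups, so difference 0.41 × 0.5 = 0.205 (printed rounded as 0.20).
- Two-sided tests, overall alpha 0.05 over 3 comparisons: 0.05/3 each, critical z 2.394.
- Enrolment: "total n=187 or ~ 50 per group after accounting for the 20% drop-out rate".
- Meaningful change: "Differences of 0.12 points and 0.22 points on the expSPPB have been shown to be small and large clinically meaningful differences, respectively".
- SAP: retention of at least 90% at 6 months and 80% at 18 months.

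**1. Reproduce the stated power.** SE = 0.5 × √(1 − 0.72²) × √(2/50) = 0.0694. Power = Φ(0.205/0.0694 − 2.394) = 71%, as in Table 3 for n = 50.

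**2. Who is missing.** 187 × 0.20 ≈ 37. With 10% lost by month 6, 187 × 0.10 ≈ 19 of them would have a 6-month value. Retention at 12 months is not given.

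**3. Predictors.** Large-sample simulation, with these assumptions (not in the documents): 10% lost at random before month 6; a further 10% lost after it by a logistic rule on 6-month change; correlation between follow-up visits 0.72 to 0.88. Baseline-adjusted ANCOVA on observed 18-month values stands in for baseline-only imputation, which has the same limit.

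| Late loss depends on 6-month change | Estimate of a true 0.205 |
|---|---|
| in neither arm | 0.205 |
| equally in both arms, same loss rate in each | 0.205–0.206 |
| one arm only, log-odds 1 per SD | 0.180–0.192 or 0.218–0.230, by arm and sign |
| one arm only, log-odds 0.5 per SD | shift of about 4–6% |

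Adding the 6-month value returns the estimate to about 0.205 in every row. When one common rule is allowed to give different loss rates by arm, a true 0.20 is estimated at 0.190–0.195.

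**4. MNAR tipping point.** Suppose missing participants in the higher-protein arm of an adjacent contrast are worse than MAR predicts by δ. The contrast falls by 0.20 × δ.
- Significance threshold: 2.394 × 0.0694 = 0.166.
- Tipping δ: (0.205 − 0.166)/0.20 ≈ 0.19 points, between the protocol's small (0.12) and large (0.22) differences.
- δ = 0.12: 0.205 − 0.024 = 0.181, power 58%. δ = 0.22: 0.205 − 0.044 = 0.161, power 47%.
- Taking 187/3 per arm, tipping δ is 0.09 at 70% retention and 0.48 at 90%.
- RecProt vs 18-mo HiProt: (0.41 − 0.166)/0.20 ≈ 1.2 points.
- Check by multiple imputation (62 per arm, 20 imputations, 1,500 replicates): δ of 0, 0.12 and 0.22 give mean estimates 0.203, 0.183 and 0.160, and power 68%, 57% and 45%.

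The same formula for the other Table 3 outcomes, adjacent contrasts, n = 50:

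| Outcome | Design difference | Threshold | Tipping δ |
|---|---|---|---|
| Knee strength (Nm) | 12.6 | 10.02 | (12.6 − 10.02)/0.20 = 12.9 |
| Lean mass (kg) | 1.1 | 0.81 | (1.1 − 0.81)/0.20 ≈ 1.4 |
| IMAT (cm³) | 4.1 | 3.00 | (4.1 − 3.00)/0.20 = 5.5 |

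Each of these needs a deficit larger than its whole design difference. An equal deficit in both arms, with equal missingness, shifts nothing.

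**The case against.** **The wording does not cause the power loss.** Informative dropout would do the same to any MAR analysis, including the one proposed here. This stands: the defect is that the sensitivity may go unreported.

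**The tipping result is particular to expSPPB.** If missing participants in the higher-protein arm kept none of the benefit, expSPPB would fall to 0.8 × 0.205 = 0.164, barely under 0.166. Knee strength (10.08 against 10.02 Nm), lean mass (0.88 against 0.81 kg) and IMAT (3.28 against 3.00) would stay above their thresholds. The expSPPB contrast tips readily because it has only 71% power, which the protocol discloses. This also stands.

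**The predictor point argues from silence.** A reader might infer that the protocol excludes interim values or arm from the imputation; it does not. Yet baseline covariates are the only predictors it names, so an analyst could follow it to the letter and leave the interim values out.

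**The determination could be a judgement from withdrawal records.** That is a fair reading, and the records are useful. They cannot establish whether unseen values are MNAR, so a conditional analysis still may not run.

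**Function and body composition belong to the parent study, and the SAP supplied is for bone.** True, but the supplied protocol itself states the rule for these outcomes, and the rule can be assessed as written.

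**Conclusion.** The point holds as a cheap and worthwhile improvement; it does not show that the trial's result will be biased.

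- **Predictors:** about half of the roughly 37 expected missing would have an unused 6-month value. Under one-arm dependence at an assumed log-odds of 1 per SD, the expSPPB contrast moves by about 6–12% in either direction. With a shared mechanism the bias is little or none.
- **MNAR:** a one-arm deficit of about 0.19 points removes significance from an adjacent expSPPB contrast at 50 completers per arm and 20% missing. The contrast between the two extreme groups is robust, and knee strength, lean mass and IMAT need more than their full design difference.

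Two stronger readings are not supported. A reader might infer that dropout does differ by arm; no section shows it, and the one-arm mechanisms above are assumptions. A reader might also extend the point to bone, as if the primary 18-month contrast were left open there. The SAP specifies ANCOVA for the 18-month primary endpoint and gives the mixed model a separate purpose, the trajectory over time.

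**What to change.** 1. State MAR as the primary assumption, without a prior determination.
2. Include in the imputation model arm, baseline, the planned baseline covariates and every observed interim value of the outcome (6 and 12 months for function and weight; 6 months for DXA and CT). Alternatively, take the 18-month contrast from a likelihood-based repeated-measures model with group-by-visit and baseline-by-visit terms and unstructured covariance.
3. Always run a delta-adjusted MNAR analysis. For expSPPB, shift imputed values by arm over at least 0 to 0.22 points in both directions, use the documented withdrawal reasons to judge which shifts are plausible, and report the tipping point.

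The cost is new wording, a little more analysis and a few covariance parameters; no new data are needed. Participants lost before month 6, about half of the expected missing, gain nothing from the added predictors, although the delta analysis covers them.
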